10.0 ADVERSE EVENT REPORTING

10.1 Adverse event is any untoward medical occurrence that may present during treatment with a pharmaceutical product but which does not necessarily have a causal relationship with this treatment.

Adverse drug reaction is a response to a drug which is noxious and unintended and which occurs at doses normally used in man for prophylaxis, diagnosis, or therapy of disease or for the modification of physiologic function.

Assessing causal connections between agents and disease is fundamental to the understanding of adverse drug reactions. In general, a drug may be considered a contributory cause of an adverse event if, had the drug not been administered, 1) the event would not have happened at all, 2) the event would have occurred later than it actually did, or 3) the event would have been less severe.

The Investigator or physician designee is responsible for verifying and providing source documentation for all adverse events and assigning the attribution for each event for all subjects enrolled on the trial.

10.2 Adverse Events (AEs) will be evaluated according to the CTC AE version 4.0 and documented in medical record. Only unexpected AEs will be recorded in the Case Report Form (CRF). PDMS/CORe will be used as the electronic case report form for this protocol. Adverse events and protocol specific data will be entered into PDMS/CORe. Expected events during leukemia therapy are:

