10.2.1 Myelosuppression related events (due to disease or leukemia therapy)

- 10.2.1.1** febrile or infection episodes not requiring management in the intensive care unit
- 10.2.1.2** epistaxis or bleeding except for catastrophic CNS or pulmonary hemorrhage
- 10.2.1.3** anemia, neutropenia, lymphopenia, thrombocytopenia, leukopenia

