10.2.2 Disease Related Events

10.2.2.1 Symptoms associated with anemia

10.2.2.1.1 fatigue

10.2.2.1.2 weakness

10.2.2.1.3 shortness of breath

10.2.2.2 electrolyte abnormalities (sodium, potassium, bicarbonate, CO₂, magnesium)

10.2.2.3 chemistry abnormalities (LDH, phosphorus, calcium, BUN, protein, albumin, uric acid, alkaline phosphatase, glucose)

10.2.2.4 coagulation abnormalities

10.2.2.5 disease specific therapy (induction, maintenance, salvage, or stem cell therapy)

10.2.2.6 alopecia

10.2.2.7 bone, joint, or muscle pain

10.2.2.8 liver function test abnormalities associated with infection or disease progression

10.2.2.9 disease progression

10.2.2.10 abnormal hematologic values

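### Section 10.2 keeps listed expected adverse events off the CRF even when possibly related to erlotinib, while Section 11.2 plans unrestricted treatment-emergent AE tables and names no other source

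*Combined protocol and SAP*

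**What the plan says.** Safety and tolerability is one of the two primary objectives (Section 1.1.2).

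On recording, Section 10.2 says that AEs "will be evaluated according to the CTC AE version 4.0 and documented in medical record", and then: "Only unexpected AEs will be recorded in the Case Report Form (CRF". It designates PDMS/CORe as the electronic CRF and adds, without the same limit, "Adverse events and protocol specific data will be entered into PDMS/CORe".

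The expected list follows. Section 10.2.1 is headed "Myelosuppression related events (due to disease or leukemia therapy" and includes "febrile or infection episodes not requiring management in the intensive care unit" and "epistaxis or bleeding except for catastrophic CNS or pulmonary hemorrhage". Section 10.2.2, on disease-related events, includes electrolyte abnormalities, "chemistry abnormalities (LDH, phosphorus, calcium, BUN, protein, albumin, uric acid, alkaline phosphatase, glucose" and "coagulation abnormalities". Section 10.3 keeps abnormal hematology values off the CRF and reports the highest or lowest abnormal chemistry value for each course.

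On analysis, Section 11.2 plans the number and percentage of treatment-emergent AEs, with breakdowns by severity and by relationship to drug. It also plans laboratory shift tables, a summary table for each parameter, and figures over time. It does not restrict the AE tables to unexpected events and does not say which data they use.

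**The concern.** The recording rule and the planned tables have different scopes. A programmer who builds the 11.2 tables from the CRF gets only the events left after the expected list has been removed, yet the tables would be titled and read as all treatment-emergent AEs.

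This matters most for the breakdown by relationship. Some listed categories are ones that an investigator could attribute at least possibly to erlotinib, and the restriction removes them before attribution can be tabulated. In a single-arm trial no control group would carry the same omission, so the reported percentages stand alone as the tolerability result.

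**Working it through.** No sample size, power or error rate in the plan depends on this point, so the check sets the sections side by side.

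1. **Is PDMS/CORe a second source?** No. Section 10.2 makes it the CRF. The restriction to unexpected AEs and the unrestricted sentence about entering AEs therefore concern the same system, and for a listed event both cannot be followed.

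2. **Is the expected list confined to unrelated events?** No.
   - The heading of 10.2.1 covers events caused by leukemia therapy, and erlotinib is the therapy under study.
   - In 10.2.2 the electrolyte, chemistry and coagulation items carry no attribution condition.
   - Other items do carry one. Liver test abnormalities are tied to infection or progression, renal failure to tumor lysis or anti-infective drugs, and rash to antibiotics. Where the list limits an item by cause, it says so.

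3. **Is 11.2 limited to match?** No. It has no restriction to unexpected AEs and no label saying that listed events are left out.

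4. **Where does each kind of event end up?** (Sections 10.1, 10.2 and 10.4, with the restriction applied as written.)

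| Event | Medical record, graded and attributed | CRF | SAE report to IND Office |
|---|---|---|---|
| Not listed (e.g. diarrhea, ILD, rash not due to antibiotics), non-serious | yes | yes | no |
| Not listed, serious | yes | yes | yes |
| Listed, serious | yes | no | yes |
| Listed, non-serious | yes | no | no |

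   The last row is the gap. Such events exist only in the source record, and no section describes extracting them for 11.2. Section 10.3 may leave a trace of an abnormal chemistry value on the CRF, but it mentions no attribution.

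5. **Effect on a table built from the CRF.** A category wholly on the list, such as coagulation abnormalities, would have no AE entries whatever happened. A category partly on the list, such as infection, would show only the remainder. The understatement equals the share of patients whose only events in that category are listed ones. The documents give no figure for that share, so no percentage is offered.

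6. **Toxicity monitoring (11.1).** The count covers clinically significant non-hematologic grade 3–4 toxicity at least possibly related to erlotinib, and 11.1 does not say where it is taken from. If it came from the CRF alone, listed events would be missed and the error would run toward not stopping. If SAE reports were also used, only non-serious listed events would be missed.

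7. **Section 10.3 (secondary).** Read literally, it removes the abnormal counts that the hematology shift tables, summaries and figures need. It would also remove counts that Section 9 needs for response: CRi is defined by neutrophils below 1.0 or platelets below 100 × 10⁹/L, and hematologic improvement starts from low pretreatment values. A reading that disables the primary endpoint is unlikely to be intended. The likelier reading is that 10.3 governs AE reporting only, but it does not say so.

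**The case against.** The strongest reply is that selective recording of expected events is a declared choice in a leukemia trial, where infection, bleeding and metabolic disturbance are common from the disease itself. Every AE is graded in the medical record, the investigator assigns attribution to each, and all SAEs go to the IND Office whether expected or not. Section 11.2 never says that the CRF is its only source. The heading of 10.2.2 could also be read as limiting its items to events caused by the disease.

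Much of this stands. It confines the gap to non-serious listed events and makes the harm conditional on how the tables are built. It does not remove the mismatch. The medical record is not named as a source for analysis, the heading of 10.2.1 expressly includes therapy, and 10.2.2 gives no instruction for a coagulation or electrolyte event that is possibly drug-related.

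It can also be said that labelling the tables would be enough. That would make them accurate, but possibly related non-serious events would still be absent from the analysis of a primary objective.

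A reader might infer three stronger points that the documents do not support:
- **That the loss can be sized from the Section 2.1.1 table**, which includes electrolyte and PT/INR events among SAEs related to erlotinib. Those are serious events from other studies, and serious events in this trial have their own reporting route. The table shows that the categories overlap, not how much would be lost here.
- **That the laboratory outputs cannot be produced.** Section 10.3 sits within AE reporting, Section 10.2 sends protocol-specific data to PDMS/CORe, and 11.2 sets no time interval that one chemistry extreme per course would fail to meet.
- **That the stopping rule is compromised.** This holds only if its count is taken from the CRF, which 11.1 does not say.

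**Conclusion.** The point holds for the AE tables and should be fixed; confidence is moderate. Following 10.2 as written and building 11.2 from the CRF would understate the listed categories, including events possibly related to erlotinib, and readers could not separate absence from non-recording. The two sentences in 10.2 about what enters PDMS/CORe also conflict and need to be reconciled.

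The conclusion assumes that the CRF is the working source for 11.2, the only system the plan designates for AE data entry, and that the list is applied without regard to attribution. The amount lost is unknown. For 10.3 the finding is only that its scope should be stated.

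**What to change.** 1. **Section 10.2:** keep entry of all unexpected AEs, and add that all non-hematologic AEs of grade 3 or higher, and all non-hematologic AEs of any grade at least possibly related to erlotinib, are entered in PDMS/CORe with grade and attribution whether or not they are listed as expected. Reword the unrestricted sentence about AE entry to agree. **Section 11.1:** state that the toxicity count uses these records together with the SAE reports.
2. **Section 11.2:** label the AE tables as covering the AEs captured under 10.2, and name what is not tabulated: listed hematologic AEs, and listed grade 1–2 non-hematologic events considered unrelated to erlotinib.
3. **Section 10.3:** state that it limits AE reporting only, and that the 11.2 laboratory outputs and the Section 9 response assessments use the dated, scheduled laboratory values.

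The cost is wording in four sections and modest extra data entry, for at most 29 patients, from records that the protocol already requires. No design parameter changes.

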10.2.4 Hospitalization for the management of any of the above expected events

10.3 Abnormal hematologic values will not be recorded on the case report form. For abnormal chemical values, the apogee or nadir (whichever is appropriate) will be reported per course on the case report form.

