10.4 Serious Adverse Event Reporting (SAE)

An adverse event or suspected adverse reaction is considered “serious” if, in the view of either the investigator or the sponsor, it results in any of the following outcomes:

- Death
- A life-threatening adverse drug experience – any adverse experience that places the patient, in the view of the initial reporter, at immediate risk of death from the adverse experience as it occurred. It does not include an adverse experience that, had it occurred in a more severe form, might have caused death.
- Inpatient hospitalization or prolongation of existing hospitalization
- A persistent or significant incapacity or substantial disruption of the ability to conduct normal life functions.
- A congenital anomaly/birth defect.

Important medical events that may not result in death, be life-threatening, or require hospitalization may be considered a serious adverse drug experience when, based upon appropriate medical judgment, they may jeopardize the patient or subject and may require medical or surgical intervention to prevent one of the outcomes listed in this definition. Examples of such medical events include allergic bronchospasm requiring intensive treatment in an emergency room or at home, blood dyscrasias or convulsions that do not result in inpatient hospitalization, or the development of drug dependency or drug abuse (21 CFR 312.32).

- Important medical events as defined above, may also be considered serious adverse events. Any important medical event can and should be reported as an SAE if deemed appropriate by the Principal Investigator or the IND Sponsor, IND Office.
- All events occurring during the conduct of a protocol and meeting the definition of a SAE must be reported to the IRB in accordance with the timeframes and procedures outlined in “The University of Texas M. D. Anderson Cancer Center Institutional Review Board Policy for Investigators on Reporting Unanticipated Adverse Events for Drugs and Devices”. Unless stated otherwise in the protocol, all SAEs, expected or unexpected, must be reported to the IND Office, regardless of attribution (within 5 working days of knowledge of the event).

- **All life-threatening or fatal events**, that are unexpected, and related to the study drug, must have a written report submitted within **24 hours** (next working day) of knowledge of the event to the Safety Project Manager in the IND Office.

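### Sections 10.2–10.3 keep expected cytopenias off the CRF even when they end treatment, so a CRF-based discontinuation table under 11.2 could miss non-serious cases

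*Combined protocol and SAP*

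**What the plan says.** **Capture.** Under 10.2, all adverse events "will be evaluated according to the CTC AE version 4.0 and documented in medical record", but the CRF is narrower: "Only unexpected AEs will be recorded in the Case Report Form (CRF". The same section says "PDMS/CORe will be used as the electronic case report form for this protocol", so the restriction applies to that system.

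**What counts as expected.** The first category is headed "Myelosuppression related events (due to disease or leukemia therapy", and item 10.2.1.3 under it reads "anemia, neutropenia, lymphopenia, thrombocytopenia, leukopenia". Item 10.2.2.10 adds "abnormal hematologic values". No grade, duration, attribution or action-taken limit is attached to these items.

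**Laboratory values.** Section 10.3 says "Abnormal hematologic values will not be recorded on the case report form". For chemistry, by contrast, it asks for the extreme value in each course.

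**Serious events.** Section 10.4 says "all SAEs, expected or unexpected, must be reported to the IND Office, regardless of attribution". Hospitalizations for expected events go into the SAE log.

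**Stopping drug.** Section 6.3, which is framed as suggestions, advises stopping erlotinib when hematologic toxicity attributed to it has not recovered within 14 days.

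**Reporting.** Section 11.2 plans a separate summary of adverse events requiring discontinuation, overall, by severity and by relationship. It does not name the data source.

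**The concern.** The protocol foresees a particular event (erlotinib stopped for an attributed cytopenia) and promises a table in which that event belongs. Its capture rule keeps the same event off the form that would ordinarily feed the table. The rule is a stated exclusion, which is more than a detail left unsaid.

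Safety and tolerability is a primary objective (1.1.2). The stopping rule in 11.1 counts only non-hematologic toxicity, so hematologic intolerance that ends treatment depends on the 11.2 summaries to be reported. A reader of the final table could see fewer treatment-ending events than the medical records contain, and the plan describes no step to reconcile the two.

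**Working it through.** The plan gives no figure to reproduce. The check is a trace of one patient through the sections, followed by simple arithmetic on what a missed case would do.

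**Trace**

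1. A patient has a cytopenia that the investigator attributes to erlotinib. It does not recover in 14 days, and erlotinib is stopped as 6.3 advises.
2. Is the event expected? Yes, under 10.2.1.3. Attribution to erlotinib does not change this, because the category heading covers events caused by leukemia therapy, and erlotinib is the leukemia therapy under study.
3. Does it go on the CRF as an adverse event? No, under 10.2.
4. Does the count reach the CRF as a laboratory value? No, under 10.3.
5. Is there another reporting route? If the event is judged serious, yes, through 10.4. If not, the only stated location is the medical record.
6. Does it belong in the 11.2 discontinuation table? Yes, with its severity and relationship. A table built from CRF adverse event records would not contain it.

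**Size**

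Inputs from section 11.0: n = 29 at full enrollment, n = 14 if the trial stops after the first stage. The documents give neither the number of cases nor their rate, so both are assumptions below.

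Shift per missed case = 1/n: 1/29 = 3.4 percentage points; 1/14 = 7.1 points.

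Worst-case contrast, assuming nobody discontinues for any other adverse event (exact Clopper-Pearson 95% intervals):

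| n | Missed cases (assumed) | Table shows | Complete record |
|---|---|---|---|
| 29 | 1 | 0% (0 to 11.9%) | 3.4% (0.1 to 17.8%) |
| 29 | 2 | 0% (0 to 11.9%) | 6.9% (0.8 to 22.8%) |
| 29 | 3 | 0% (0 to 11.9%) | 10.3% (2.2 to 27.4%) |
| 14 | 1 | 0% (0 to 23.2%) | 7.1% (0.2 to 33.9%) |

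Chance of at least one case = 1 − (1 − p)^n, where p is the assumed true rate of non-serious, erlotinib-attributed cytopenia ending treatment:

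| p (assumed) | n = 29 | n = 14 |
|---|---|---|
| 1% | 25.3% | 13.1% |
| 5% | 77.4% | 51.2% |
| 10% | 95.3% | 77.1% |

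**The case against.** The other side has a good case on reach.

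- **The data source is not fixed.** Section 11.2 does not say its tables come from the CRF. The response criteria in 9.1 need neutrophil and platelet counts, and 11.2 plans summaries for each laboratory parameter, so some hematology data must reach the analysis despite 10.3. This stands, and it makes the finding conditional. Counts alone, however, would not show that a cytopenia was attributed to the drug or was the reason for stopping.
- **Section 10.2 also says in general terms that adverse events and protocol-specific data are entered in PDMS/CORe.** That might include an off-treatment reason; the CRF fields are not in the documents, so its absence cannot be shown. But the sentence states no exception to the specific limit on unexpected events, and a bare reason would not supply the severity and relationship that the table needs.
- **Nothing is lost at source.** The medical record holds every event, and 10.1 requires the investigator to document and attribute each one. This stands: what is missing is an instruction to transcribe.
- **The non-serious remainder may be small.** Section 10.4 gives blood dyscrasias without hospitalization as an example of important medical events that may be treated as serious. Some treatment-ending cytopenias would be reported that way, but this rests on judgment and does not cover all of them.
- **Cases may be few.** Section 6.1 plans no interruption for myelosuppression in the first 4 weeks and lets treatment continue despite low counts when blasts persist. Its guided holds concern responders or patients with no marrow leukemia. At the 20% target, responders number 0.20 × 29 = 5.8. If cases arise mainly among them, the 10% row above (2.9 patients) means about half of responders stopping for this reason, which is high. The 6.3 advice is not formally limited to these patients.
- **Cytopenia is background in AML.** That is a sound reason not to record every one. It does not extend to an event the investigator has attributed to erlotinib and acted on by stopping it.

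**Conclusion.** The point holds in a limited form. As written, 10.2 and 10.3 exclude erlotinib-attributed cytopenias from the CRF with no exception for those that end treatment. A discontinuation table built from CRF adverse event records would omit such events when they are not reported as SAEs.

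Two conditions are needed: the table is drawn from those records, and at least one such case occurs. The documents settle neither. If no case occurs, the table is correct. The one general result on size is the 1/n shift per missed case, 3.4 points at n = 29 and 7.1 at n = 14. The contrasts with 0/n are a worst case, because 6.2 provides for stopping erlotinib for rash, diarrhea, interstitial lung disease and other toxicities, and such events not on the expected list would still appear.

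A reader might infer more, but the documents do not support it:

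- *That treatment-ending cytopenias go unreported altogether.* Serious ones reach the IND Office whether expected or not, and all are in the medical record.
- *That the table will be wrong.* Neither its source nor the number of cases is known.
- *That trial decisions are affected.* The overall response rate, the two-stage rule and the toxicity boundaries do not use these records; the boundaries count only non-hematologic events.
- *That 6.1 and 6.3 conflict.* They can be read together as a hold with a 14-day cap.

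This is a low-priority improvement to the completeness of safety reporting on a primary objective.

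**What to change.** Add one sentence to 10.2 and repeat it in 10.3:

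*Exception: any adverse event, expected or not, including cytopenia, that leads to discontinuation of erlotinib is recorded on the CRF with grade, relationship and dates.*

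This supplies the items that the 11.2 table needs and leaves the exclusion of background cytopenias in place. Sections 6.1 and 6.3 can stay as they are. The cost is one extra CRF entry per affected patient. Treatment rules, sample size, response rule and toxicity boundaries do not change.

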10.2.1 Myelosuppression related events (due to disease or leukemia therapy)

- 10.2.1.1** febrile or infection episodes not requiring management in the intensive care unit
- 10.2.1.2** epistaxis or bleeding except for catastrophic CNS or pulmonary hemorrhage
- 10.2.1.3** anemia, neutropenia, lymphopenia, thrombocytopenia, leukopenia

10.2.2 Disease Related Events

10.2.2.1 Symptoms associated with anemia

10.2.2.1.1 fatigue

10.2.2.1.2 weakness

10.2.2.1.3 shortness of breath

10.2.2.2 electrolyte abnormalities (sodium, potassium, bicarbonate, CO₂, magnesium)

10.2.2.3 chemistry abnormalities (LDH, phosphorus, calcium, BUN, protein, albumin, uric acid, alkaline phosphatase, glucose)

10.2.2.4 coagulation abnormalities

10.2.2.5 disease specific therapy (induction, maintenance, salvage, or stem cell therapy)

10.2.2.6 alopecia

10.2.2.7 bone, joint, or muscle pain

10.2.2.8 liver function test abnormalities associated with infection or disease progression

10.2.2.9 disease progression

10.2.2.10 abnormal hematologic values

10.2.3 General Therapy Related Events

10.2.3.1 catheter related events

10.2.3.2 renal failure related to tumor lysis syndrome or antibiotic/antifungal therapy

10.2.3.3 rash related to antibiotic use

